7.6.2 Serious Adverse Events and Adverse Event Leading to Discontinuation

Summaries of worst grade of on-study SAE, both by individual grade (1, 2, 3, 4, or 5, together with an Any Grade category) and by grade grouped as “Any, Grade 3-4 and Grade 5” will also be presented. This last summary will be repeated for:

- On-study drug-related SAEs
- On-study AEs leading to discontinuation.
- Drug related AEs leading to discontinuation

By-subject listings of SAEs and AEs leading to study drug discontinuation will be produced.

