7.4.1.1 Duration of Study Therapy

The number of cycles of treatment received by subjects will be summarized (using n, mean, STD, median, min, max, q1 and q3) by treatment group. A summary of the number of subjects taking each drug in each cycle will also be presented by treatment group.

The duration of each treatment (elotuzumab, dexamethasone [oral and IV combined] and pomalidomide), in months, will be calculated as:

$$(date\ of\ last\ dose\ of\ the\ drug - date\ of\ first\ dose\ of\ the\ drug + 1) / 30.4375$$

Duration of each of the study treatments will be summarized by treatment group.

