7.5.3 Analysis of Overall Survival

Overall survival is another secondary objective. It will be compared between arms using a stratified log-rank test procedure with a two-sided, $\alpha = 0.2$ level. The stratification factors will be the same as those used for the analyses of PFS and tumor response. The OS function for each randomized arm will be estimated using the Kaplan-Meier product-limit method. Median and two-sided 95% confidence intervals for median OS will be computed by randomized arm.

All analyses performed for PFS (detailed in [Section 7.5.1](#)) will be repeated for OS. Supportive analyses of PFS (detailed in [Section 7.5.1.1](#)) as well as the subset analyses (detailed in [Section 7.5.1.2](#)) will also be repeated for OS.

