7.6.1 Adverse Events

AEs will be categorized using the most recent version of the MedDRA, by system organ class (SOC) and preferred term. The severity of AEs will be graded using the NCI CTCAE (v 3.0).

On-study AEs are defined as non-serious and serious AEs with an onset date on or after the first dose until 60 days after the last dose. See [Section 8.4](#), Imputing AE Onset Dates, for a discussion of imputation rules for incomplete or missing AE onset dates. If the relationship to study drug is missing, then the AE will be assumed to be related to study drug.

Unless specified otherwise, AEs will be counted only once per subject within each SOC and preferred term, according to their worst CTC grade.

Tables will be sorted by SOC and preferred term, with SOCs ordered by decreasing frequency overall and then alphabetically. Preferred terms will be sorted within SOCs by descending frequency overall and then alphabetically. The sorting will be done based on the total column when arms are presented side-by-side.

The following summaries will be presented by treatment arm:

Frequency tables of the worst grade of on-study AE will be presented: one table with AEs broken out by individual grade (1, 2, 3, 4 or 5) and an Any Grade category and another table in which both arms are included and grades are grouped as follows "Any, Grade 3-4 and Grade 5." The last summary will be repeated for:

- On-study drug-related AEs.
- On-study AEs that occurred \leq Cycle 2 and \geq Cycle 3.

A by-subject listing of all AEs will be presented.

- Exposure-adjusted AE incidence rates (including multiple occurrences of unique events) will be calculated for each SOC and preferred term.

Exposure-adjusted incidence rate per 100 person-years will be used and will be calculated as:

$$100 \times \left(\frac{\text{Total number of unique AEs}}{\frac{\text{subject date of last dose of study drug} - \text{subject date of first dose of study drug} + 60 + 1}{365.25}} \right)$$

and will be displayed along with a count of events

For these additional tables, AEs can be counted multiple times within each SOC and preferred term.

A by-subject listing of unique AEs will be provided.

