7.6.3.3 Second Primary Malignancies

A summary table and a by-subject listing of second primary malignancies (SPM) will be provided. In addition, exposure-adjusted SPM incidence rates (including multiple occurrences of unique events) will be presented by treatment group and will be calculated as follows:

$$100 \times \frac{\text{Total number of unique SPM events}}{\left(\frac{\text{subject death date or last known alive date} - \text{subject date of first dose of study drug} + 1}{365.25} \right)}$$

Information on SPM will be obtained from the on-treatment eCRF page for secondary malignancies and the “Survival Status” eCRF page.

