7.6.5 Deaths

The number and percentage of deaths and the investigator-reported cause of death will be presented by treatment group. This will be summarized for all deaths, and for those reported on study treatment or within 60 days of discontinuing study treatment.

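### SAP 7.6.2 gives SAEs and AEs leading to discontinuation only crude worst-grade frequencies, without the Cycle 2/3 split or exposure-adjusted rate of 7.6.1, so longer E-Pd treatment alone would produce a small crude excess

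*SAP*

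**What the plan says.** SAP 7.6.2 summarises SAEs by worst grade: "Summaries of worst grade of on-study SAE, both by individual grade" and in grouped form (any, 3-4, 5). The grouped table is repeated for drug-related SAEs, for "On-study AEs leading to discontinuation", and for drug-related AEs leading to discontinuation. By-subject listings follow. The visible section has no rate and no split by period.

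SAP 7.6.1, for all on-study AEs, plans both. "Exposure-adjusted AE incidence rates (including multiple occurrences of unique events) will be calculated for each SOC and preferred term", per 100 person-years. The grouped-grade table is also repeated for "On-study AEs that occurred" up to Cycle 2 and from Cycle 3. On-study AEs there include serious ones and run from first dose to 60 days after last dose.

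SAP 7.6.3.3 fits the denominator to the event: "exposure-adjusted SPM incidence rates (including multiple occurrences of unique events) will be presented by treatment group", with time counted to death or last known alive date.

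Other visible text bears on exposure. In SAP 7.4.1.1, "Duration of each of the study treatments will be summarized by treatment group". The protocol synopsis continues treatment to progression or unacceptable toxicity. SAP 5.1 sets the PFS medians at 4.0 and 6.8 months, and SAP 7.5 makes the PFS analysis, after at least 71 events, the basis of the study report.

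**The concern.** A crude proportion with at least one event rises with time at risk. If elotuzumab delays progression as designed, E-Pd patients stay on treatment longer and have more time to record a first SAE or a discontinuation AE. The E-Pd column would then be higher even if the two regimens were equally toxic per month.

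The SAP deals with this for AEs overall and for second primary malignancies, but does not carry it to these two categories. The 7.6.1 rates cannot fill the gap: they pool serious with non-serious events by SOC and preferred term and count repeat occurrences, so no SAE or discontinuation rate can be read from them. A reader would have to weigh the crude tables informally against the treatment-duration table.

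At stake is how two prominent tolerability results of an open-label add-on trial are read. No visible test or decision rule uses them.

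**Working it through.** **Design figure first.** SAP 5.1 states 71 PFS events for HR 0.57, two-sided alpha 0.2 and 85% power. Schoenfeld: 4(1.2816 + 1.0364)²/(ln 0.57)² = 68.0, so 69. Freedman: (1.2816 + 1.0364)² × (1.57/0.43)² = 71.6, so 72. The stated 71 is reproduced within rounding.

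**Inputs from the documents.** Exponential PFS with medians 4.0 and 6.8 months (SAP 5.1); 114 subjects at 13 per month, so accrual takes 114/13 = 8.77 months; cut-off at 71 events (SAP 7.5) or about month 15 (9 + 6, SAP 5.1); a 60-day tail, d = 60/30.4375 = 1.97 months (SAP 7.6.1).

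**Assumptions.** 57 per arm; treatment ends only at progression; no loss to follow-up; equal constant event hazards h of 0.02, 0.05 and 0.10 per month in both arms. The documents give no event hazards, hence the range.

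**Timing of the cut-off.** With λ = ln 2/median and follow-up F uniform on (T − 8.77, T), expected events are 57 × the sum over arms of E[1 − exp(−λF)]. At T = 15 this is 57 × (0.825 + 0.650) = 84. It equals 71 at T ≈ 12.2: 57 × (0.714 + 0.532). The planned month 15 belongs to a plan that allows about 10% loss, so both cut-offs are shown.

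**Crude risks.**
- SAE: 1 − exp(−hd) × E[λ/(λ+h) × (1 − exp(−(λ+h)(F−d))) + exp(−(λ+h)(F−d))]
- Discontinuation AE (on treatment only): E[h/(λ+h) × (1 − exp(−(λ+h)F))]
- Standard error of the difference: √[p₁(1−p₁)/57 + p₂(1−p₂)/57]

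| Cut-off | h | SAE: Pd v E-Pd | Excess, points (in SE) | Discontinuation: Pd v E-Pd | Excess, points (in SE) |
|---|---|---|---|---|---|
| 71 events, month 12.2 | 0.02 | 10.2% v 11.5% | 1.3 (0.23) | 7.8% v 9.7% | 2.0 (0.37) |
| | 0.05 | 23.2% v 25.9% | 2.7 (0.34) | 17.8% v 22.0% | 4.3 (0.57) |
| | 0.10 | 40.2% v 44.2% | 4.0 (0.44) | 31.1% v 37.8% | 6.7 (0.76) |
| Month 15 | 0.02 | 11.7% v 13.9% | 2.2 (0.35) | 8.9% v 11.7% | 2.8 (0.50) |
| | 0.05 | 26.2% v 30.6% | 4.3 (0.51) | 19.9% v 25.9% | 5.9 (0.75) |
| | 0.10 | 44.4% v 50.5% | 6.1 (0.65) | 34.1% v 42.9% | 8.9 (0.98) |

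**Sensitivity at month 15, same three hazards.** If the hazard falls to a quarter after 56 days, the excess is 0.6, 1.3 and 2.3 points (SAEs) and 0.9, 2.1 and 3.7 points (discontinuation). With an added 0.03 per month of stopping for other causes, it is 1.8, 3.7 and 5.3, and 2.4, 5.0 and 7.5.

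**Would the split help?** Two cycles are 56 days, or 1.84 months. The SAE risk 1 − exp(−1.84h) is the same in both arms, because the 60-day tail covers the whole period. Discontinuation risk, h/(λ+h) × (1 − exp(−1.84(λ+h))), is 3.1% v 3.3%, 7.5% v 8.0% and 14.4% v 15.4%, so the artefact is at most about 1 point.

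**Would a rate help?** Under equal constant hazards the first-event rate ratio is 1.00 for SAEs with the 60-day window and 1.00 for discontinuation with on-treatment time. A 60-day tail on the discontinuation denominator would give 1.11 to 1.12, so the denominators must differ.

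**The case against.** The strongest case against is that most of the control exists. SAEs and discontinuation AEs enter the 7.6.1 rates and split, duration is tabulated by arm, and listings are planned. This stands as a limit on the point: what is missing is a separate view of two subsets. A reader might infer that the SAP has no exposure-adjusted safety analysis; SAP 7.6.1 and 7.6.3.3 show otherwise. Nor does the point extend to severe AEs or deaths. The 7.6.1 split shows Grade 3-4 and Grade 5. For mortality, SAP 7.5.3 says "It will be compared between arms using a stratified log-rank test procedure", and SAP 7.6.5 tabulates all deaths and "those reported on study treatment or within 60 days of discontinuing study treatment".

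A second objection is that a crude proportion is a legitimate quantity, namely how many patients given each regimen have an event by the cut-off, and that any lean is against the experimental arm. That is right, and the crude tables should stay. They do not separate longer treatment from greater toxicity.

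Third, the sponsor safety conventions (SAP 8.6) and the Data Presentation Plan (SAP 8.7) are not visible and may add these tables. If they do, a cross-reference in 7.6.2 is enough. The point concerns what 7.6.2 itself says.

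Fourth, a rate can mislead. In the same model with assumed hazards of 0.15 per month for 56 days and 0.05 afterwards in both arms, the rate ratio is 0.94 (SAEs) and 0.92 (discontinuation) despite equal toxicity. With an early E-Pd hazard of 0.20 (true early ratio 0.20/0.15 = 1.33) it shows only 1.14 and 1.13. The part of the split up to Cycle 2 shows that harm directly: 24.1% v 30.8% and 20.8% v 28.2%. This stands, and is why the split leads. The part from Cycle 3 still carries the exposure difference.

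Finally, 7.6.2 does not say whether discontinuation means one drug or all. Protocol 4.5.3 lets components stop separately, and E-Pd has three drugs that can be stopped against two. That also stands, and the fix has to settle it.

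**Conclusion.** The gap holds as a minor, optional improvement. Under the design medians and equal monthly toxicity, the crude tables would lean against E-Pd by about 1.3 to 4.0 points for SAEs and 2.0 to 6.7 points for discontinuation AEs at the 71-event cut-off. The month-15 figures, 2.2 to 6.1 and 2.8 to 8.9 points, are the upper end for the study-report analysis, because the same model has 84 events by then.

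Every value is below one standard error of the arm difference. The sizes rest on assumed constant hazards, 57 per arm, and treatment ending only at progression; clustering of events early in treatment makes them smaller.

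A reader might go further and infer that the trial would misjudge the safety of E-Pd. The documents do not support that: the tables feed no visible test or stopping rule, and the effect is on descriptive interpretation.

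**What to change.** In SAP 7.6.2:

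1. Repeat the Cycle 2/3 split for SAEs and for AEs leading to discontinuation, and name the part up to Cycle 2 as the main exposure-comparable view.
2. Beside it give, by arm and as descriptive rows only, a first-event rate per 100 person-years for (a) any SAE, with time at risk ending at the earliest of first event, 60 days after last dose, death or data cut-off; and (b) AEs leading to discontinuation of all study drugs, with on-treatment time ending at the earliest of first event, last dose of any study drug, death or data cut-off, and no 60-day tail.
3. State in the text that (b) refers to stopping all study drugs.
4. Keep the crude tables.

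The cost is SAP wording, two split tables and two rate rows from dates already collected. The first-event rate is a new derivation, since 7.6.1 counts repeat events over last dose minus first dose plus 61 days; 7.6.3.3 is a precedent for a denominator fitted to the event.

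The rates will be imprecise. At h = 0.05 and month 15, expected events are 15.0 and 17.4 (SAEs) and 11.4 and 14.7 (discontinuation), so exp(1.96 × √(1/n₁ + 1/n₂)) gives 95% limits about 2.0-fold and 2.2-fold each way. Because a constant-hazard rate can dilute early harm, it should not be read without the split.

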7.6.3 Adverse Events of Special Interest

7.6.3.1 Infusion Reaction

Infusion reaction is a known elotuzumab toxicity. It will be based on investigator assessment and will be defined as any non-serious or serious adverse event judged by the investigator to be infusion related and which also occurs on the day of or the day after the elotuzumab infusion. These summaries will be presented:

- Frequency tables of the worst grade of on-study investigator infusion reaction (any grade and grade 1 through 5) by treatment group. The same summary will be presented with grades grouped as Any, Grade 3-4 and Grade 5.
- Frequency tables of the worst on-study investigator infusion reaction SAE will be also summarized by treatment group as above.
- Frequency of infusion reaction by infusion rate.
- Frequency of infusion reaction by elotuzumab concentration
- Frequency of infusion reaction by cycle.

By-subject listings of infusion reactions will be produced.

7.6.3.2 Opportunistic Infections

Multiple myeloma is associated with immune dysfunction and the natural course of the disease includes increased infection risk. In addition, elotuzumab may inhibit some cellular components of the immune system. Therefore, a thorough characterization of infections will be presented. Infections will be based on the SOC ‘infections and infestations’ and opportunistic infections will be based on clinically pre-defined PT terms ([Appendix 2](#)):

- Time to onset and duration of first infection
- Frequency of infections including opportunistic infections by treatment group.
- Absolute lymphocyte count at time of first infection
- Kinetics of lymphocyte reduction

7.6.3.3 Second Primary Malignancies

A summary table and a by-subject listing of second primary malignancies (SPM) will be provided. In addition, exposure-adjusted SPM incidence rates (including multiple occurrences of unique events) will be presented by treatment group and will be calculated as follows:

$$100 \times \frac{\text{Total number of unique SPM events}}{\left(\frac{\text{subject death date or last known alive date} - \text{subject date of first dose of study drug} + 1}{365.25} \right)}$$

Information on SPM will be obtained from the on-treatment eCRF page for secondary malignancies and the “Survival Status” eCRF page.

7.6.4 Safety in Subgroups

Summaries of all adverse events with $\geq 5\%$ frequency, adverse events leading to discontinuation, serious adverse events (any grade), and death within 60 days of last dose will be presented for the levels of the factors listed below.

In addition summaries by the same factors will be produced for second primary malignancies, opportunistic infections and infusion reactions.

- Age:
 - < 65
 - ≥ 65 up to < 75
 - ≥ 75 years
- Gender (male, female)
- Race (White, Black, Asian, Other)
- High risk vs. low risk vs. other standard

- Region (North America, Europe, Japan, and Rest of World)
- Number of prior lines of therapy (2-3 vs. ≥ 4)
- ECOG PS (0 vs. 1 or 2)

The sorting will be the same as for the overall table (not by subgroup).

7.6.5 Deaths

The number and percentage of deaths and the investigator-reported cause of death will be presented by treatment group. This will be summarized for all deaths, and for those reported on study treatment or within 60 days of discontinuing study treatment.

7.6.6 Clinical Laboratory Evaluations

On-treatment laboratory tests for safety are defined as those that occur after first dose of any study therapy until 60 days after last dose of any study therapy.

The number and percentage of subjects with each worst severity grade for on-study hematology parameters (hemoglobin, WBC, ANC, ALC and platelets) will be presented, by treatment group. Grades will be categorized as Grade 1, Grade 2, Grade 3, Grade 4, Any Grade and Grade 3-4. Subjects will be counted only once for each parameter, according to their worst post baseline CTC grade. The percentage of subjects with each worst severity grade will be calculated out of the number of treated subjects with on-study assessment for lab parameter. Subjects with a no post-baseline (on-treatment) assessment for a lab parameter will be reported in the “NOT REPORTED” category.

This summary will be repeated for:

- Liver parameters (ALT, AST, alkaline phosphatase, albumin and total bilirubin) with available CTC grades
- Renal/electrolyte parameters (sodium, potassium, bicarbonate, calcium, glucose and creatinine) with available CTC grades

Sodium, potassium, calcium, and random glucose will be presented separately, based on their high and low values.

For blood urea nitrogen (BUN), direct bilirubin and total protein the worst category on-treatment will be presented. Results will be categorized as: below upper normal limits, above upper normal limits or not reported.

For reporting purposes, urea will be converted to BUN, using the conversion factor: $\text{urea (mmol/L)} / 0.357 = \text{BUN (mg/dL)}$.

Subjects experiencing any potential drug induced liver injury (DILI) will be summarized by treatment group and overall as follows:

- A summary of the number and percentage of subjects with (AST or ALT > 3 x upper limit of normal (ULN)) and (Total bilirubin > 2 x ULN and ALP < 2 x ULN) will be presented.

If any potential cases of DILI are identified then clinical review will be conducted to ensure no other immediate apparent possible causes of AT elevation and hyperbilirubinemia are present, including but not limited to, viral hepatitis, pre-existing chronic or acute liver disease, or the administration of other drugs known to be hepatotoxic.

Note: The timing for total bilirubin rising to $> 2 \times$ ULN needs to be concomitant with or within 30 days after ALT or AST rising to $> 3 \times$ ULN. ALP needs to be $< 2 \times$ ULN at the time of or within 2 weeks before ALT or AST rising to $> 3 \times$ ULN or TBILI $> 2 \times$ ULN. This mean a normal ALP value ($\leq 2 \times$ ULN) must be present within 2 weeks of either the ALT/AST criteria or the TBILI criteria.

A by subject listing of all laboratory data will be provided. A separate listing will be provided for all subjects potentially experiencing DILI.

7.6.7 Echocardiogram, MUGA Scan and Electrocardiograms

A by subject listing of electrocardiogram (ECG) data collected at screening will be presented.

7.6.8 Vital Signs, Physical Measurements

Vital signs parameters (body temperature, seated diastolic and systolic blood pressure and heart rate) will be presented by visit and time point in a subject listing.

7.7 Pharmacokinetic Analysis

Elotuzumab concentrations taken pre (elotuzumab) dose and post-end of infusion, at each scheduled visit, will be summarized, by cycle and day, for subjects in the elotuzumab arm only. In addition to the standard summary statistics, the geometric mean and % CV will also be presented.

A by subject listing of elotuzumab concentrations will be provided.

7.8 Anti Drug Antibody Analysis

ADA status of a sample:

- Baseline ADA positive sample: ADA is detected in the last sample prior to the first dosing date/time of elotuzumab.
- On study ADA positive sample: after the first dosing date/time of elotuzumab:
 - ADA is detected in a subject whose baseline is negative
 - ADA is detected and ADA titer is at least 9-fold or greater (\geq) than the baseline positive ADA titers
- On study ADA negative sample: after the first dosing date/time of elotuzumab, no ADA detected relative to baseline or with a titer lower than the baseline sample.

Anti-drug antibody (ADA) will be summarized for elotuzumab arm only with the following categories:

- Baseline ADA Positive Subject: A subject with Baseline ADA Positive Sample

- **ADA Positive Subject:** A subject with at least one ADA positive sample after the first elotuzumab dose relative to baseline.
 - **Persistent Positive:** ADA positive sample at 2 or more sequential timepoints at least 3 months apart
 - **Only the Last Sample Positive:** ADA positive sample only in the last sampling timepoint.
 - **Other Positive:** not persistent positive with ADA negative sample in the last sampling
- **ADA Negative Subject:** A subject with no ADA positive sample after the first elotuzumab dose relative to baseline.

A by subject listing of all ADA data at each time-point will be provided along with corresponding elotuzumab concentration values measured as a part of pharmacokinetic assessments.

7.9 Pharmacogenomic Analysis

The relationship between elotuzumab effect on PFS and high risk cytogenetic abnormality will be explored through Cox regression modeling. The following analyses may be conducted depending on the number of subjects with available biomarker data in the trial. A separate model will be produced for each of the following FISH/cytogenetic abnormalities, which will be categorized as positive/negative:

- t(4:14)
- t(14:16)
- del 17p
- del(1q)
- del(1p)
- t(6:14)

Each model will contain treatment, FISH factor and a term for treatment by FISH/cytogenetic factor interaction. If treatment by FISH/cytogenetic factor interaction is not significant at the five percent level it will be excluded from the model. In addition, the treatment effect (median PFS along with corresponding HRs, and 95% CIs) may be computed separately, in the positive and negative groups. A similar analysis may be conducted to evaluate the effect on ORR using a logistic regression model.

Similar analyses, as described above, will be conducted to evaluate the relationship between baseline SLAMF7 expression on MM cells and NK cells with efficacy (PFS or ORR).

The level of SLAMF7 protein expression at baseline and at progression, and the change in SLAMF7 level, from baseline to progression, will be summarized, by arm, using descriptive statistics.

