7.5 Efficacy

Efficacy analyses (PFS, ORR and OS) will be conducted on the population of all randomized subjects, grouped by arm assigned at randomization, unless otherwise noted.

Unless stated otherwise, whenever a stratified analysis is specified, the stratifications factors will be those used in the randomization (per IVRS), that is:

- Number of prior lines of therapy (2-3 vs. ≥ 4)
- ISS Staging at study entry (I-II vs. III)

The final analysis of PFS will occur after at least 71 progression events have been observed. This analyses will serve as the basis for the clinical study report. The final analysis of OS will be conducted after at least 78 deaths have been observed.

All p-values reported will be 2-sided. The alpha (α) level used for the two-sided CI will be same as nominal significance level for hypothesis testing ($\alpha = 0.2$). In addition two-sided 95% CI for these endpoints will also be provided. The p-values presented in the clinical study report will be rounded to the fourth decimal place. Point estimates and confidence bounds for efficacy variables will be rounded to the second decimal place.

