7.5.1 Primary Analysis of Progression-Free Survival

The primary objective of this study is to compare PFS (based on the primary definition) across the two randomized arms. A two-sided $\alpha = 0.2$ log-rank test, stratified by number of lines of prior therapy (2-3 vs. ≥ 4) and ISS Staging at study entry (I-II vs. III) will be used to compare the PFS of subjects randomized to E-Pd to that of subjects randomized to Pd.

A stratified Cox proportional hazard model for PFS with treatment arm as single covariate will be used to report the hazard ratio of E-Pd to Pd and its corresponding 80% (and 95%) CI. The stratification factors will be the same as those used in the randomization.

The PFS function for each treatment arm will be estimated using the KM product limit method and will be displayed graphically. Median PFS will be estimated via the KM curve. Two-sided 95% CI for the median PFS will be computed for each randomized arm by the Brookmeyer and Crowley method using the log-log transformation of the survivor function.

The method of Gail and Simon¹² will be used to test for a qualitative interaction between treatment and strata, number of lines of prior therapy (2-3 vs. ≥ 4) and ISS Staging at study entry (I-II vs. III). This test will be conducted at the $\alpha = 0.10$ level and using the HR as estimate for treatment effect.

The proportional hazards assumption will be assessed via the following hazard rate model, which contains a time dependent covariate:

$$\lambda(t, z) = \lambda_i(t) e^{\{(b_1 + b_2 \times [\log(t)]) \times Z\}}, \quad i = \{1 - 4\}$$

where $i = 1 - 4$ corresponds to each of the four levels the stratum can take, and Z is the treatment indicator, which is equal to 1 for the combination arm and 0 for the control arm. The transformation of time is $\log(t)$. The null hypothesis, that the proportional hazards assumption is valid, i.e., that $b_2 = 0$, will be tested against the alternative hypothesis that $b_2 \neq 0$ using a Wald statistic.

Sensitivity analyses of PFS will also be conducted based on the secondary definition of PFS. These analyses will be the same as those specified above in [Section 7.5](#), Primary Analysis of PFS.

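### The exploratory biomarker models in SAP 7.9 leave out both randomization factors, so a marker associated with ISS stage would have its main effect partly confounded by stage; the primary hazard ratio and the treatment-by-marker interaction are not materially affected

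*SAP*

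**What the plan says.** SAP 7.9 gives the aim of the FISH analyses: "The relationship between elotuzumab effect on PFS and high risk cytogenetic abnormality will be explored through Cox regression modeling". They are optional: "The following analyses may be conducted depending on the number of subjects with available biomarker data in the trial". A separate model is fitted for each of six abnormalities: "Each model will contain treatment, FISH factor and a term for treatment by FISH/cytogenetic factor interaction". The interaction is then screened: "If treatment by FISH/cytogenetic factor interaction is not significant at the five percent level it will be excluded from the model". A parallel logistic analysis of ORR may be run. The same kind of analysis is planned, without the optional wording, for the relationship of baseline SLAMF7 expression on myeloma cells and NK cells to PFS or ORR.

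Elsewhere the SAP says whether a model is stratified:

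- **7.5 (general convention):** "whenever a stratified analysis is specified, the stratifications factors will be those used in the randomization (per IVRS), that is" prior lines (2-3 vs ≥4) and ISS stage (I-II vs III).
- **7.5.1 (primary):** "A stratified Cox proportional hazard model for PFS with treatment arm as single covariate will be used to report the hazard ratio of E-Pd to" the control arm.
- **7.5.1.1 item 1 (multivariate model):** the randomization factors are kept as strata, with high myeloma risk among the covariates.
- **7.5.1.2 (subset forest plots, including individual FISH abnormalities):** explicitly unstratified.
- **7.5.2 (ORR):** a CMH test stratified by the same factors.

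**The concern.** The 7.5 convention says which factors to use once a stratified analysis has been specified. Section 7.9 does not specify one, so as written its models omit ISS stage and prior lines.

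FISH status and SLAMF7 expression are not randomized. The sponsor stratifies by ISS and combines ISS with FISH in its myeloma risk category (7.3.3, 7.5.1.2), so it evidently regards both as prognostic. If a marker is more common in ISS III, a model holding only treatment and marker gives the marker part of the effect of stage, and a marker with no effect of its own could look prognostic. For SLAMF7 the marker-efficacy association is itself the stated question.

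Omitting prognostic factors also pulls a Cox treatment hazard ratio slightly toward 1. Part of any difference between the 7.9 and 7.5.1 treatment estimates would then come from the choice of model.

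**Working it through.** **1. The plan's own figure.** Section 7.9 has no sample-size figure, so the check starts from the PFS design in SAP 5.1: 71 events, HR 0.57, two-sided α = 0.2, 85% power (1:1 allocation assumed).

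- Schoenfeld: 4(1.282 + 1.036)² / (ln 0.57)² = 68.0, so 69 events.
- Freedman: (1.282 + 1.036)² × (1.57/0.43)² = 71.6, so 72 events.
- Power at 71 events: 86.1%.

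The stated 71 events reproduce.

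**2. Effect of leaving out the strata.** Exponential PFS was simulated with 30,000 to 60,000 subjects per scenario, to approximate the large-sample value of each estimate.

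- From the SAP: control median 4.0 months (used for the reference stratum), treatment HR 0.57, 9 months' accrual plus 6 months.
- Assumed, because the documents give none of these: marker prevalence 20%; true marker HR 1.00; no true interaction; 40% with ≥4 lines, unrelated to the marker; HR 1.5-2.5 for ISS III; HR 1.0-1.5 for ≥4 lines; ISS III in 45-60% of marker-positive and 25% of marker-negative subjects (linked), or 30% in both (not linked).

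Selected scenarios (unstratified is 7.9 as written; stratified is by stage × lines):

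| HR ISS III | HR ≥4 lines | ISS III share, marker +/− | Marker HR, unstratified / stratified | Treatment HR, unstratified / stratified | Interaction ratio, unstratified |
|---|---|---|---|---|---|
| 1.5 | 1.0 | 30% / 30% | 1.002 / 1.002 | 0.582 / 0.576 | 0.981 |
| 1.5 | 1.0 | 45% / 25% | 1.083 / 1.001 | 0.577 / 0.571 | 1.010 |
| 2.0 | 1.0 | 60% / 25% | 1.264 / 1.011 | 0.593 / 0.573 | 1.012 |
| 2.0 | 1.5 | 60% / 25% | 1.254 / 0.996 | 0.588 / 0.555 | 1.064 |
| 2.5 | 1.5 | 30% / 30% | 0.977 / 0.972 | 0.608 / 0.571 | 1.029 |
| 2.5 | 1.5 | 60% / 25% | 1.339 / 1.001 | 0.613 / 0.575 | 1.007 |

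Across all 13 scenarios run:

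- Marker HR (truth 1.00): 1.08-1.34 unstratified when linked to stage and 0.98-1.00 when not; 0.97-1.02 stratified.
- Treatment HR (truth 0.57): 0.58-0.61 unstratified; 0.56-0.58 stratified.
- Interaction ratio of HRs (truth 1.00): 0.98-1.06 unstratified, with no consistent direction.

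**3. Size at 71 events.** For a marker of 20% prevalence, SE(log HR) ≈ 1/√(71 × 0.2 × 0.8) = 0.297. The marker bias of ln 1.08 = 0.077 to ln 1.34 = 0.293 is 0.26 to 0.99 SE. A 5% test of the null marker's main effect would therefore reject about 6% to 17% of the time. For treatment, SE ≈ 2/√71 = 0.237, and the largest shift, ln(0.61/0.57) = 0.068, is about 0.3 SE.

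**4. How often the main-effects model is the one reported.** SE of the log interaction ratio ≈ √(4/(71 × 0.2) + 4/(71 × 0.8)) = 0.593. The 5% test has 80% power only at a ratio of exp(−(1.960 + 0.842) × 0.593) = 0.19 (0.11 at 10% prevalence, 0.23 at 30%). At a true ratio of 0.5, z = 0.693/0.593 = 1.17 and power is about 21%, so the term is dropped about 79% of the time. With no interaction it is dropped about 95% of the time.

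**The case against.** **The marker main effect is not what 7.9 asks.** For FISH this is largely right: the question is effect modification, and the interaction barely moves. But step 4 shows that the interaction will usually be dropped, leaving treatment and marker as the reported model. For SLAMF7 the marker-efficacy relationship is the stated question.

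**The marker-stage link is assumed.** This stands. Because the risk category pairs ISS with FISH, a reader might infer that the SAP expects adverse cytogenetics to travel with ISS III. The pairing shows only that both are thought prognostic. The high-risk definition also groups ISS II with III, unlike the randomization split, and nothing in the documents links SLAMF7 to stage.

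**The plan handles this elsewhere.** Section 7.5.1.1 item 1 adjusts for one composite risk factor within strata; it gives no estimate for individual abnormalities and none for SLAMF7. Items 3 and 4 do show how far stratification moves the overall treatment HR, which lessens the comparability concern.

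**Silence is not exclusion.** A stratified model need not list its strata as terms, and 7.9 does not say that its three terms are the only ones. The Protocol's biomarker analysis section (8.4.5 in the contents) and some SAP text before 7.2 are redacted, so the gap can be asserted only for the visible text. There, however, the SAP normally says when it stratifies.

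**Stratifying fits rare markers badly.** This is also right, and it is why the fix uses covariates.

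**Conclusion.** The visible text of 7.9 omits ISS stage and prior lines, and no other visible rule supplies them. The consequence is minor and conditional. A null marker's HR of about 1.08 to 1.34 arises only under an assumed link with stage and the assumed prevalence and prognostic HRs in step 2; without a link there is essentially no bias. No figure was computed for the ORR logistic models.

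Two stronger readings are not supported. One is that the trial's treatment effect is diluted. The treatment HR of record comes from the stratified 7.5.1 model, which is untouched; the shift to 0.58-0.61 occurs only in the 7.9 models, and it is ordinary attenuation from omitted prognostic covariates, not confounding, because treatment is randomized within strata. The other is that the predictive-marker conclusions are biased: the interaction ratio stays at 0.98-1.06. For that question, the low power of the 5% interaction test is the larger limitation.

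**What to change.** Amend the model sentence in SAP 7.9 to read: *Each Cox and logistic model will contain treatment, the marker, their interaction, and the two randomization factors (prior lines 2-3 vs ≥4; ISS I-II vs III, per IVRS) as covariates.* Add that the two factors stay in the model when the interaction is removed, and that the SLAMF7 models follow the same form.

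Use the covariate form throughout. Rare markers make four strata sparse, and a switch from strata to covariates when data look thin would be a data-dependent choice. The check above fitted the stratified form; because the two factors act proportionally in the simulated data, the covariate form estimates the same quantities there.

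The cost is one sentence, two variables already recorded in the IVRS, and two extra parameters in small exploratory models. The adjusted results will also differ in form from the unstratified FISH subset estimates in 7.5.1.2, which a table footnote can explain.
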